8.1 Primary Objective

The primary objective of the DUS is to estimate the dose and duration of eliglustat therapy as well as the proportion, therapeutic class, and duration of past and concomitant medication use in patients treated with eliglustat. The concomitant medications of interest (CMI) are strong and moderate CYP2D6 inhibitors, strong and moderate CYP3A inhibitors, strong CYP3A inducers, P-gp substrates and CYP2D6 substrates (Appendix 1 in Section 14.1). Simultaneous use of strong or moderate CYP2D6 inhibitors with strong or moderate CYP3A inhibitors concomitantly with eliglustat will be explored, if feasible.

8.2 Secondary Objective

The secondary objective of the DUS is to describe the healthcare service pattern (i.e., prescriber's specialty and types of patient visit) for the prescriptions of concomitant medications in patients treated with eliglustat. The relevance of prescriber's specialty and types of patient visit is to inform whether prescriptions to GD1 patients are made in hospital or in outpatients services, and to inform on the number of health professionals taking care of these patients.

8.3 Exploratory Objective

There are no exploratory objectives planned for this study. However, CMI use will be described in greater detail and by drug therapeutic class which could improve the understanding of eliglustat usage patterns in the four included European countries. The prescriber specialty and the type of patient visit will also be analysed for eliglustat deliveries.

9 RESEARCH METHODS

9.1 Study Design

The DUS of eliglustat will be undertaken in a series of prescription databases covering large populations to provide useful and reliable investigations of diseases as rare as Gaucher Disease. This DUS will be based on secondary use of data. This DUS is descriptive only with no comparative elements.

The study shall take the form of a cohort study using electronic health records. Gaucher Disease Type 1 patients identified in each prescription database who are being prescribed eliglustat will be followed from one year before their first prescription of eliglustat to the end of the study in Q3 2024. During this period, all prescriptions of past and CMI will be recorded (Appendix 1 in Section 14.1). The study will rely entirely on analysis of secondary data as described in the initial study synopsis submitted in the Risk Management Plan (RMP).

9.1.1 Primary Endpoints

The primary outcomes of interest include the dose of eliglustat, the duration of eliglustat use, and the use of specific CMI one year before the first delivery of eliglustat and during the use of eliglustat.

Similarly to eliglustat, the CMI use will be identified through the Anatomical Therapeutic Chemical Code (ATC), country-specific coding system or through the mention of the CMI in the patient's chart. The list of medications of interest is described in Appendix 1 in Section 14.1).

9.1.2 Secondary Endpoints

The secondary endpoints include prescriber's specialty corresponding to the delivered drugs (general practitioner [GP], haematologist, oncologist, ophthalmologist, rheumatologist, surgeon, etc.) and visit type corresponding to the delivered drug (e.g., in city, in hospital, in specialised care centres, etc.).

9.1.3 Exploratory Endpoints

The exploratory endpoints include drug therapeutic class of CMI used to prior to and during the use of eliglustat, as well as prescriber speciality and type of visit for the eliglustat deliveries.

9.1.4 Rationale for the Study Design

A pilot study conducted in Regione Lombardia in 2015 has demonstrated the feasibility of using high-quality, population-based regional/national prescription databases for drug utilisation evaluation of concomitant medications (Appendix 3 [Section 14.3]). This study took the form of a twelve-month retrospective study of the drug prescriptions in GD1 patients before eliglustat became available.

9.2 Setting

9.2.1 Study Period

The study period will begin from one year before the first prescription of eliglustat in each data source to the end of the study.

The date of the first prescription of eliglustat will vary between data sources since the launching/reimbursement of eliglustat is different in each country (see Section 9.4). In any case, the first prescription will be after the date of approval of eliglustat by the EMA that is 19 January 2015.

The exposure period for one patient will be defined as the period between the exposure start date (date of the first record of eliglustat prescription) and the exposure end date, i.e., the date of the last eliglustat prescription plus the duration of eliglustat use according to the last prescription or the end of the study or the death of the patient if it occurs before the end of the study.

The end date of the study period will also vary between data sources since different time-lag exist between the time of prescription/delivery of drugs and availability of these data in databases. Consequently, in case of a two-year time-lag, data extracted in 2022 will have been collected until 2020 thus, the study period will end in 2020.

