9.7.1 General Considerations

The exposure period for one patient corresponds to the period of eliglustat use. This period will be defined as the period between the exposure start date (the first record of eliglustat prescription) and the exposure end date (end of study or date of the last eliglustat prescription plus the duration of eliglustat use according to the last prescription or death date).

The statistical analyses will be only descriptive and will include the following:

• Descriptive analysis of eliglustat therapy in terms of duration and dose.

- Descriptive analysis of the past medication use (one year prior to the exposure period) in terms of proportion, therapeutic class and duration. The treatments of interest will be (details in Appendix 1 in Section 14.1):
 - Strong and moderate CYP2D6 inhibitors (CMI1 and CMI2)
 - Strong and moderate CYP3A inhibitors (CMI3 and CMI4)
 - Simultaneous use of strong or moderate CYP3A inhibitors with strong or moderate CYP2D6 inhibitors (CMI1 + CMI2 + CMI3 + CMI4)
 - Strong CYP3A inducers (CMI5)
 - P-gp substrates (CMI6)
 - CYP2D6 substrates (CMI7)

The proportions will be computed taking into account all treatments of interest and also by type of treatments and by duration. Proportions for the group CYP inhibitors will be also computed. The duration will be treated as a continuous variable and also as a categorical variable. The categorical variable will be defined as follow: 1. Total use will be defined as any prescription whatever the duration; 2. Chronic use will be defined as total duration of single or consecutive prescriptions of 15 days or over.

If the number of GD1 patients allows it, stratified analyses based on gender and age groups will be performed as well as analyses by year.

- Descriptive analysis of the concomitant medication use (i.e., during the exposure period) in terms of proportion, therapeutic class and duration. The treatments of interest will be the same as for the past medication use. The proportions will be computed as for the past medication use that is considering all treatments and also by therapeutic class and duration.
- Descriptive analysis of the health care service pattern (i.e., prescriber's specialty and types of patient visit) for the use of concomitant medications.

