9.7.3.3 Concomitant Medications

To analyse the use of concomitant medications, two study periods will be determined:

- 1. The one-year period before the first delivery of eliglustat.
- 2. The period during eliglustat use which will span from the first delivery of eliglustat to the last delivery of eliglustat plus the duration of supply.

The analyses described in the following sections will be conducted separately for each of the two periods.

9.7.3.3.1 **Proportion of Patients with CMI**

Proportion of patients with CMI will be computed considering all CMI, by therapeutic class of CMI (CMI1 to CMI7), and separately for the group of CYP inhibitors (CMI1 to CMI4). Also, proportion of patients that have taken a strong or moderate CYP2D6 inhibitor simultaneously with a strong or moderate CYP3A inhibitor will be explored, if feasible.

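### The exposure window is one unbroken first-to-last eliglustat span, so an interacting drug supplied during a treatment interruption counts as concomitant, and the interruption may count as eliglustat use

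*Protocol*

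**What the plan says.** Section 9.2.1 opens exposure at the first recorded eliglustat prescription and closes it at "the date of the last eliglustat prescription plus the duration of eliglustat use according to the last prescription", with end of study and death as alternative ends. Section 9.7.1 repeats that end ("date of the last eliglustat prescription plus the duration of eliglustat use according to the last prescription or death date") and adds: "The exposure period for one patient corresponds to the period of eliglustat use". Section 9.7.3.3 sets the window for the concomitant-medication analysis. It works from deliveries instead of prescriptions but keeps the same shape: the window will "span from the first delivery of eliglustat to the last delivery of eliglustat plus the duration of supply".

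Section 9.7.1 also fixes what counts as concomitant: "Descriptive analysis of the concomitant medication use (i.e., during the exposure period) in terms of proportion, therapeutic class and duration".

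None of the three definitions has a permissible gap, treatment episodes or removal of uncovered time. Deliveries between the first and the last play no part in the window. Section 9.7.3.2 averages the duration of eliglustat use and bands it at one and two years, without a formula. By contrast, section 9.7.3.3.2 builds the duration of each CMI category from all of its deliveries.

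**The concern.** A first-to-last span equals time on drug only if supply is continuous. For a patient who interrupts and restarts, the rule treats the interval as exposed. Any CMI delivered in it then enters the numerator for use during eliglustat, and the interval may also enter eliglustat duration. Section 9.1.1 names both quantities as primary outcomes.

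The direction matters because of the purpose in section 8: to judge whether risk minimisation leads to avoidance of significant interactions. If eliglustat was interrupted while an interacting drug was supplied, the two drugs did not overlap, yet the rule records concomitant use. The measure cannot then tell co-exposure from separation in time. The same applies to the exploratory analysis of CYP2D6 and CYP3A inhibitors used together during eliglustat.

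**Working it through.** **Plan's own figure.** None depends on this rule, so there is nothing to reproduce. The protocol gives no interruption frequency, gap length, days of supply per eliglustat delivery or yearly CMI risk. Everything below is assumed and illustrative.

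**1. Eliglustat duration, if taken from the span.** Overstatement = gap / (span − gap).

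| Span | 30-day gap | 90-day | 180-day | 365-day |
|---|---|---|---|---|
| 730 days | 4.3% | 14.1% | 32.7% | 100% |
| 1,095 days | 2.8% | 9.0% | 19.7% | 50.0% |
| 1,460 days | 2.1% | 6.6% | 14.1% | 33.3% |

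Example: 365 / (1,095 − 365) = 50.0%, which is 36 months recorded against 24 covered. Bands can change too. A 730-day span with a 180-day gap has 550 covered days, so the patient is recorded at two years or more instead of one to under two.

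As a limiting case, assume two 28-day supplies delivered 730 days apart. The span is 730 + 28 = 758 days against 56 supplied, a ratio of 13.5.

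**2. Chance of at least one CMI counted as concomitant.** Assume a constant yearly risk *p*, the same on and off eliglustat, with a 36-month span and 12 months off drug.

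- *p* = 20%: span 1 − 0.8³ = 48.8%; covered time 1 − 0.8² = 36.0%; difference 12.8 points.
- *p* = 10%: span 1 − 0.9³ = 27.1%; covered time 1 − 0.9² = 19.0%; difference 8.1 points.

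**3. A rate anchored on the pilot (Appendix 3, section II.4).** There, 10 of 48 patients (20.8%) on other Gaucher drugs had a CYP inhibitor. The text refers to 2008-2009 and the Table 4 footnote to 2008-2012, so I read the figure over 2 and over 5 years. Rate = −ln(1 − 10/48) / years = 0.1168 or 0.0467 per year. Probability = 1 − exp(−rate × time), with a 3-year span.

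| Gap | 2-year reading: covered → span | 5-year reading: covered → span |
|---|---|---|
| 90 days | 27.5% → 29.6% | 12.1% → 13.1% |
| 180 days | 25.4% → 29.6% | 11.1% → 13.1% |
| 365 days | 20.8% → 29.6% | 8.9% → 13.1% |

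**4. Cohort effect.** If 10% to 30% of patients had the 12-month gap at *p* = 20%, the proportion would rise by 0.128 × 0.10 = 1.3 points to 0.128 × 0.30 = 3.8 points. Results are reported by source (section 9.7.1), with 87, 10, 11 and 20 patients expected in France, Denmark, Germany and Israel (section 9.5). One misclassified patient moves those proportions by 1.1, 10.0, 9.1 and 5.0 points.

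**The case against.** **Detail may sit in the SAP.** Sections 9.3 and 9.7 leave variable detail to the SAP and the country dataset specifications, which are not available here. Grace periods and overlap rules are often set there. This stands for the fine detail, but not for the window, which the protocol fixes three times. A SAP that split it into episodes would depart from the protocol.

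**Duration.** A reader might infer that eliglustat duration is certainly overstated. The protocol does not establish that. Section 9.7.1 equates the exposure period with eliglustat use, but section 9.7.3.2 gives no formula, and the SAP could sum supplies. That would correct duration and leave the concomitant window as it is.

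**Size.** The year-long gap is the most severe of the single gaps tabulated. With pilot-based rates, a 90-day gap adds only about 1 to 2 points for an affected patient. Eliglustat is described as long-term treatment, so gaps may be uncommon. A cohort shift of 1.3 to 3.8 points is also small beside sampling error: the 95% half-width at 36% is 1.96 × √(0.36 × 0.64 / 87) = 10 points in France and 21 points with n = 20. This stands as a limit on importance, but imprecision does not excuse a one-directional error.

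**Two further inferences do not hold.** A reader might conclude that correct avoidance is scored as a failure. The study is descriptive (section 9.1) and has no pass or fail measure; the risk is misreading. A reader might also see the same rule in the pilot. Table 4 there follows a 2008-2009 cohort over a fixed calendar period, which is a different construction.

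**Conclusion.** The concern holds for the concomitant window. As written, sections 9.2.1, 9.7.1 and 9.7.3.3 count a CMI supplied in an eliglustat interruption as concomitant. It holds conditionally for eliglustat duration, if that is taken from the exposure period. Against covered time, both errors can only go upward, and they blur the avoidance that section 8 wants assessed.

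The size cannot be derived from the protocol. It is zero without interruptions and affects only patients who stop and restart. The illustrations (50% on duration; 36.0% to 48.8% on CMI) rest on an assumed 12-month gap in a 36-month span and, for CMI, a 20% yearly risk equal on and off drug. They are not estimates for this cohort.

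**What to change.** Amend sections 9.2.1, 9.7.1 and 9.7.3.3 together:

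- Build eliglustat episodes from every delivery (date plus supply), before the local step in section 9.6 that reduces the data to one row per patient.
- Count a CMI as concomitant only when its supply overlaps days covered by eliglustat supply. Use no grace period in the main CMI analysis, with pre-specified permissible gaps as sensitivity analyses. A grace period in the main analysis would still count short pauses as exposed, and 8 of the 10 pilot inhibitor users received the antibiotic clarithromycin.
- State the formula in section 9.7.3.2: eliglustat duration is time in episodes under a pre-specified gap.
- Keep the first-to-last span as a secondary measure, labelled as time since start.

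No new collection should be needed, since section 9.4 describes delivery or dispensing data in all four sources. The cost is added programming and dependence on the supply and gap assumptions. Without a grace period, a late refill looks like a short interruption. A pause within a dispensed supply stays invisible under any delivery-based rule. Where records are incomplete, notably the Danish charts (section 9.4), an apparent gap may be a missing record. Reporting the retained span beside the episode result would show how much depends on this.

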9.2.2 Inclusion Criteria

The study population will include all GD1 patients, of all ages, with at least one recorded prescription of eliglustat over the study period in the selected databases.

Since eliglustat is indicated for GD1 only and there are no specific diagnostic/International Classification of Diseases and related health problems, 10t^h edition (ICD-10) codes for this condition, all patients with at least one recorded prescription of eliglustat during the study period will be considered to have GD1 diagnosis.

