9.2.3 Exclusion Criteria

Not applicable.

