Maccabi Healthcare Services is the second health provider in Israel which counts 2.5 million members (about 27% of the Israel population). It is a state mandated organisation with medical records fully computerised since 1993. Membership is accessible to everyone; it is free and independent of status of employment, occupation and location. This healthcare database gathers data going back 30 years on demographic characteristics, mortality and emigration, all physician diagnoses, medical visits records, hospitalisation, laboratory results, prescribed and dispensed medications, and other services delivered to patients (e.g., scans and images). Due to the high cost of eliglustat, all GD patients treated with this medication are fully compensated by the government.

Of note, there is no time-lag between the prescription/delivery of drugs and availability of these data in the database. Therefore, if the data extraction occurs in December 2022, all data recorded until this date will be available for the study.

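### In GePaRD and Maccabi, past CMI use is computed over the year before the first eliglustat record without requiring that the patient was observable in that year

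*Protocol*

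**What the plan says.** - **Entry.** Section 9.2.2 takes all GD1 patients "with at least one recorded prescription of eliglustat over the study period in the selected databases". Section 9.2.3 (Exclusion Criteria) reads "Not applicable". Section 9.5 adds that all patients with GD1 who take eliglustat go into the analysis.
- **Start and end of exposure.** Section 9.2.1 starts exposure at the "date of the first record of eliglustat prescription". It ends at "the date of the last eliglustat prescription plus the duration of eliglustat use according to the last prescription or the end of the study", or at death. Entering or leaving the database plays no part.
- **Look-back.** Section 9.7.3.3 defines the first of its two windows as "The one-year period before the first delivery of eliglustat". Section 9.7.1 plans a "Descriptive analysis of the past medication use (one year prior to the exposure period) in terms of proportion, therapeutic class and duration". Past use is part of the primary objective (Section 8.1) and a primary endpoint (Section 9.1.1).
- **Sources (Section 9.4).** The French SNDS covers about 99% of the population. Danish Gaucher patients are all followed at one hospital. GePaRD pools four statutory insurers, about 20% of Germany. Maccabi is one health provider with about 27% of the Israeli population, and "Membership is accessible to everyone; it is free and independent of status of employment, occupation and location".
- **Bias.** Section 9.9 allows for under-reporting and misclassification from missing information. It otherwise denies any source of bias that could affect the results, and it discounts selection bias because the sources are described as nationally representative. Incomplete look-back is not mentioned.

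**The concern.** A fixed one-year look-back is valid only for patients whose records cover that year. Followed as written, the protocol also applies it to patients who entered the database less than a year before their first eliglustat record. Drugs dispensed before entry are not in the source, so those months are read as months without CMI. Section 9.8.1 plans no imputation, and no passage restricts the denominator.

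A second group is patients who were already taking eliglustat when they joined. Their first record in the database is not their first use. Their start date is late, their eliglustat duration (Section 9.7.3.2) is too short, and part of their past year is treated time.

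Both groups can arise in GePaRD and Maccabi, because a person can live in Germany or Israel, and be on treatment, without being in those data. At stake are a primary endpoint and the duration table in two of the four sources. Each source is reported separately (Section 9.7.1), so the larger French source cannot dilute the effect.

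**Working it through.** **1. Expected patients (Section 9.5).** 87 (SNDS) + 10 (Denmark) + 11 (GePaRD) + 20 (Maccabi) = 128, which reproduces the protocol's figure. Partial-coverage sources: 11 + 20 = 31, and 31/128 = 24.2%. The other two: 97/128 = 75.8%.

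**2. Is the calendar start of the data the cause?** No. GePaRD data start in 2004 and Maccabi records have been computerised since 1993. Eliglustat was launched in April 2015 in Germany and January 2017 in Israel. Any gap comes from an individual's entry date.

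**3. Direction.** Let p be the true one-year proportion with CMI, f the share of a source's patients without a full year observed, and L the days they were observed. With a constant rate λ = −ln(1 − p)/365, the all-patient proportion is expected to read

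observed = (1 − f)·p + f·(1 − exp(−λL)).

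For L < 365 the second bracket is below p, so the error is downward for any f > 0.

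**4. Scale, under assumptions.** The documents give neither f nor L. For p, I use the Appendix 3 pilot, 10/48 = 20.8%, for scale only: it covers CYP inhibitors, in patients on other Gaucher treatments, over a period longer than one year. Then λ = −ln(0.7917)/365 = 0.00064 per day.

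| f | L = 0 | L = 90 days | L = 182 days |
|---|---|---|---|
| 5% | 19.8% | 20.1% | 20.3% |
| 10% | 18.8% | 19.3% | 19.8% |
| 20% | 16.7% | 17.8% | 18.9% |
| 30% | 14.6% | 16.3% | 17.9% |

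The relative error runs from −2% to −30%. If p were 50%, with half a year observed, 1 − exp(−λL) = 0.293, and the reading would be 47.9%, 45.9% or 43.8% for f = 10%, 20% or 30%.

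**5. One patient.**
- A true user wholly missed: 1/11 = 9.1 points in GePaRD, 1/20 = 5.0 points in Maccabi.
- An affected patient whose use is unknown costs less in expectation. With p = 20.8% and 182 days observed, the loss is 0.208 − 0.110 = 0.098, or 0.9 points at n = 11 and 0.5 points at n = 20. With nothing observed, the loss is 0.208, or 1.9 and 1.0 points.

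**6. Denominator after restriction.** If only these two sources lose patients, the total is 97 + 31·(1 − f).

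| f | GePaRD | Maccabi | All sources |
|---|---|---|---|
| 5% | 10.4 | 19.0 | 126.5 |
| 10% | 9.9 | 18.0 | 124.9 |
| 20% | 8.8 | 16.0 | 121.8 |
| 30% | 7.7 | 14.0 | 118.7 |

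**The case against.** **This belongs in the SAP.** Sections 9.3 and 9.7 send detailed definitions to the SAP and the country-specific dataset specifications, and no sentence spells out the past-use denominator. Either document could add a look-back flag. That stands in part. However, the protocol itself fixes entry without exclusions, puts all patients in the analysis, dates start from the first record and denies other bias. Section 9.1 describes follow-up from one year before the first prescription, which presumes that the year is observed but does not require it.

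**No patient is shown to lack look-back.** True. Open membership at Maccabi shows that people can join, not how many do.

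**The expected error is small beside sampling error.** At p = 20.8% the standard error is √(0.208 × 0.792/11) = 12.2 points in GePaRD and 9.1 points in Maccabi (n = 20), against 1.0 to 2.1 points of error at f = 10%. This stands as to size. The error is nevertheless one-directional and avoidable.

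**Stronger readings that the documents do not support.**
- *All four sources are affected.* SNDS coverage leaves little room for late entry. In Denmark all Gaucher patients attend one hospital; the stated weakness there is incomplete charts, which can touch both windows and which an enrolment rule does not cure.
- *The gap creates a false rise in CMI use after starting eliglustat.* Section 9.1 rules out comparative elements and Section 9.7.3.3 analyses the two windows separately. They differ in length, so their ever-use proportions are not directly comparable even with full look-back. Patients who transfer in also lose earlier treated time from the during-use window, so the net direction of a before/during contrast is not certain.

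**Conclusion.** The point holds for GePaRD and Maccabi, about 31 of the 128 expected patients. There, the past-use proportion is understated in expectation whenever a patient lacks a full observed year, and eliglustat duration is understated for anyone who transfers in on treatment. The direction follows from the definitions. The size cannot be derived from the documents: the tabulated errors rest on an assumed share affected, an assumed observed time, a constant rate and a borrowed prevalence. The figures of 9.1 and 5.0 points apply only to a true user who is missed altogether.

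This does not invalidate the study. It is an avoidable bias in a primary endpoint for two separately reported sources, and Section 9.9 should not exclude it.

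**What to change.** 1. In Section 9.7.3.3, compute past-use proportions and durations in patients with at least 365 days of documented enrolment before the first eliglustat record. Show the all-patient figure as a sensitivity analysis. A further condition of no eliglustat record in that year would add nothing, because start is already defined as the first record.
2. Keep every patient in the eliglustat dose and duration analyses and in the during-use analyses.
3. In the duration table, flag patients whose first eliglustat record comes soon after database entry as possible prevalent users.
4. Report per source how many patients lack the look-back, subject to the small-cell rule in Section 10.4.
5. Reword Section 9.9 to name incomplete look-back and late-dated start as possible biases in GePaRD and Maccabi.

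**Cost.** One enrolment flag and a few sentences. The past-use denominator becomes somewhat smaller (roughly 126 to 119 of 128 if 5% to 30% of patients in these two sources are affected). Some counts may be suppressed in sources this small. The restricted figure also assumes that patients with a full year are representative of the rest. The protocol does not list enrolment dates among its variables, so the data holders must confirm that they can supply them. Danish chart completeness needs separate treatment.
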